Mini International Neuropsychiatric Interview for the DSM-5 (MINI)(59): Structured interview to determine Axis I psychiatric conditions based on DSM-5 criteria.	Psychiatric History	х				
Patient Health Questionnaire Nine (PHQ9)(60): Self-Report measure of depressive symptoms.	Depressive Symptoms	х		х		
Time Line Follow Back (TLFB)(61) and Clinical Opioid Withdrawal Scale (COWS)(57): The TLFB is a validated measure quantifying drug use; average daily morphine equivalents will be calculated. The COWS is a validated measure quantifying withdrawal severity.	Opiate Use and Withdrawal	х				
Subjective Opioid Withdrawal Scale (SOWS) (68): The SOWS is a validated self-administered measure of opioid withdrawal.	Opiate Withdrawal	х	x			
The Barratt Impulsiveness Scale (BIS11) (69): The BIS is a validated questionnaire designed to assess the personality/behavioral construct of impulsivity.	Impulsivity	х				
The Pittsburgh Sleep Quality Index (PSQI) (70): Validated instrument used to measure the quality and patterns of sleep in adults.	Sleep	х		Х		
Work Productivity and Activity Impairment Questionnaire (71): The Work Productivity and Activity Impairment (WPAI) questionnaire is a well validated instrument to measure impairments in work and activities.	Functional Impairment	х		х		
The Rand 36 Item Short Form Health Survey (73): Validated self-report to assess quality of life.	Quality of Life	х		х		
Aim 1: Cue induced Craving: Primary ou paradigm.						
Prescription Opiate Craving Scale (21): Three item opiate craving scale. The three-item scale will also be administered at 1 and 4 week follow-	Provoked Opiate Craving	Х	X			

ups, but there will be no cue provocation.							
Aim 2: Pain Outcomes: Primary outcome: Change score in thermal pain threshold and pain tolerance.							
Mechanical, Thermal, and DNIC Pain Assessment: See description above.	Quantitative Sensory Assessment	x	x				
Brief Pain Inventory (23) and McGill Pain Questionnaire (24): Self report measures assessing severity, functional impairment, and affective components of pain. Administered daily during the acute phase of the study and at both follow-up visits.	Subjective Pain	х	x	x			
Exploratory Aims: Substance Use: Primary outcome: Abstinence over the final two weeks of the study, as defined by no self-reported use and a negative final urine drug screen. Executive function/inhibitory control: Will be measured using two validated computer tasks.							
Urine Drug Screen	Objective Substance Use	Х		x			

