Time Line Follow Back (61): See above.	Subjective Substance Use	х		x			
South Carolina Prescription Monitoring Program: Online database of all controlled substance prescriptions filled in the state of South Carolina.	Filled Prescription Opiates				х		
The "GoGo/NoGo" task: Participants are instructed to press a button in response to common (gray colored circles: 75% of trials) and rare (yellow colored circles: 12.5% of trials) Go stimuli and inhibit responding to rare NoGo stimuli (blue colored circles: 12.5% of trials). The task provides errors of omission and reaction times during Go trials, controls for novelty detection during processing of rare Go trials (yellow circles) and errors of commission on NoGo trials (blue circles).	Inhibitory Control						
Delayed Discounting Task: Participants will decide between a series of theoretical monetary rewards (exe: smaller rewards now, or larger rewards later) in a brief computerized task.	Delayed Discounting	х	x				

DATA MANAGEMENT AND STATISTICAL ANALYSIS: Data will be managed using REDCap. DATA MANAGEMENT AND STATISTICAL ANALYSIS: Data will be managed using REDCap. Randomization: Participants will be randomized to active or sham rTMS. Urn randomization will be used to ensure balance on three pre-specified covariates: depression status (HRSD at baseline ≥16 indicating moderate or greater depression), self-reported pain over the past three months, and planned use of replacement therapy following discharge. Statistical Analysis: Changes in study outcomes will be estimated and analyzed using several approaches. When parametric modeling assumptions can be made, changes over time will be compared between treatment groups (active rTMS vs. sham rTMS) using general linear mixed models (GLMMs). The

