GLMMs will allow us to estimate group-specific changes over time and overall effect sizes, along with the variation in those measures, while controlling for relevant baseline covariates (e.g. baseline craving, morphine equivalents, withdrawal). In an attempt to determine whether rTMS impacts craving and pain by reducing depressive symptoms, we will also examine models that do and do not control for changes in depression scores. Although we will likely not be powered to detect between-group differences in binary outcomes (i.e. drug use), such effects will be explored using generalized mixed models, and for time-to-event data (e.g. days to first opioid use), survival analysis models will be constructed. When parametric modeling assumptions do not appear to be valid, alternative (e.g. non-parametric) approaches will be used to estimate treatment efficacy and its precision. Primary outcomes will also be analyzed for evidence of differential treatment effects in subgroups determined by gender, race, and ethnicity. Post-hoc exploratory analyses using GLMMs within the active rTMS group will address whether specific characteristics (e.g. demographics, baseline craving, morphine equivalents, withdrawal) are associated with a better treatment effect. The subgroup-specific treatment effects and corresponding confidence intervals will be constructed and will be interpreted in terms of their clinical, rather than statistical, significance. Sample Size Justification: A total of n=40 participants (n=20 per arm) will be recruited. We anticipate that <20% of study participants will withdraw from the study or be lost to follow-up, meaning that ≥ n=32 participants are expected to complete the study. This sample size ensures that group-specific changes will be able to be estimated in a precise fashion, with 95% confidence intervals extending ~0.5 standard deviation units. Similarly, the overall effect size confidence interval will likely extend only 0.3 standard deviation units. As an exploratory and developmental R21 project, we recognize that our final sample size may not result in a fully powered study design. Nevertheless, our sample size will provide >80% power to detect large effect sizes (equivalent to a Cohen's d of 1.0), assuming 2-sided hypothesis testing and an alpha level of 0.05. Our preliminary work and work of others suggests that differences of this magnitude may be present within our proposed sample. For example, for Aim 1, recent investigations have found large effect sizes, with (20) reporting a d=0.84, and (18) reporting a d=0.98. For Aim 2, our recent single session study reported a d=0.65. Model based means and variability estimates will be derived from unadjusted and adjusted analyses and will be vital for designing a larger, more definitive trial in the context of a subsequent R01 submission. Relapse, Drop-Out and Clinical Deterioration: Every effort will be made to re-engage participants who miss appointments. Clinical deterioration, such as exacerbation of psychiatric or substance use disorder, will be assessed on a case-by-case basis and appropriate referral will be made. Participants will be considered drop outs if they do not come back for follow-up visits after three attempts to contact. With the exception of participants who formally withdraw from the study, we will attempt to assess early terminators at the time of discontinuation and at the post-treatment time points. These participants will be considered in the intent-to-treat efficacy analyses. Strategies to Ensure a Robust and Unbiased Approach: The proposed study will achieve robust and unbiased results via several design features including: explicit inclusion/exclusion criteria; randomization of treatment condition; the use of a validated sham control; use of validated laboratory and interview/self-report measures and methods; explicit hypotheses and corresponding planned statistical analyses; power estimates; planned handling of retention/attrition and missing data; and careful consideration of potential confounds. All experimental details are reported in a detailed manner to support replication. Consideration of gender as a biological variable: Though this trial is not powered to detect gender differences, we will perform our analysis using gender as a potential covariate. Should there be a potential gender difference found, we will use that data to power a larger trial

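### Reconcile the urn's depression factor (HRSD) with the schedule (PHQ-9), and name each outcome's own baseline, then the urn factors, in the primary models

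*Combined protocol and SAP*

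**What the plan says.** All references are to the Combined protocol and SAP, section D.

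- **Randomization.** "Urn randomization will be used to ensure balance on three pre-specified covariates". The first is "depression status (HRSD at baseline ≥16 indicating moderate or greater depression". The others are pain reported for the preceding three months and intended replacement therapy after discharge. Only depression has a stated cut-off.
- **Schedule of Visits and Assessments.** The depressive-symptom row is "Patient Health Questionnaire Nine (PHQ9)(60): Self-Report measure of depressive symptoms", marked at baseline and at the follow-up visits. The MINI is also listed at baseline, as a diagnostic interview. There is no HRSD row.
- **Schedule, Aim 2.** "Primary outcome: Change score in thermal pain threshold and pain tolerance".
- **Statistical Analysis.** In general linear mixed models, "changes over time will be compared between treatment groups", "while controlling for relevant baseline covariates (e.g. baseline craving, morphine equivalents, withdrawal". Change in depression score and gender are mentioned separately as possible adjustments.
- **Sample Size Justification.** "Model based means and variability estimates will be derived from unadjusted and adjusted analyses", to inform a later, larger trial. Power is stated as above 80% at d=1.0 with about 32 completers. For the pain aim: "For Aim 2, our recent single session study reported a d=0.65".

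**The concern.** There are two gaps, both cheap to close now.

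The first concerns allocation. The urn needs each participant's depression status before assignment. The randomisation text takes it from one instrument, the schedule collects another, and no rule maps the PHQ-9 to the HRSD cut-off. An allocation factor cannot be redefined once participants have been assigned.

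The second concerns the primary models. Craving's own baseline is offered as an example covariate, but thermal pain's is not, and none of the three balancing factors is named. The plan does not say whether baseline enters as a covariate or as a response. If it is a response, the plan does not say whether the arms share a common baseline mean. The choice affects precision, and precision matters in a trial whose estimates are meant to design the next one.

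**Working it through.** **Inputs from the documents:** 40 randomised 1:1, at least 32 completers (16 per arm), two-sided alpha 0.05, d=1.0 for power, d=0.65 for Aim 2.

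**Assumed, not in the documents:** pre-post correlation ρ; R², the share of post-baseline residual variance explained by the urn factors; d=0.65 read in change-score SD; each urn factor binary with prevalence 0.5.

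**1. The plan's own figure.** At 16 per arm and d=1.0, power is 80.7% (normal approximation) or 78.1% (noncentral t). The required n is 16 per arm, and 32/(1−0.20)=40. The statement reproduces to within 2 points.

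**2. Change score against own-baseline adjustment.** With equal variances σ²:

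- Var(post−pre) = 2σ²(1−ρ).
- Residual variance given baseline = σ²(1−ρ²).
- Ratio = (1−ρ²)/[2(1−ρ)] = (1+ρ)/2, which is 0.65/0.75/0.85 at ρ 0.3/0.5/0.7.
- Noncentrality of the change score at d=0.65: 0.65×√(16/2) = 1.84. On 30 df, power is 42.9%. The 95% half-width is 2.042×√(2/16) = 0.72 SD.
- Dividing 1.84 by √ratio gives 2.28/2.12/1.99. On 29 df, power is 59.7/53.7/48.7%.

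This closed form ignores chance baseline imbalance and unequal arms, so it is slightly optimistic.

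**3. Simulation.** Urn on three factors, 40 randomised, random loss to 32, ordinary least squares, 12,000 trials per setting (Monte Carlo SE about 0.45 points). Power (%) at d=0.65:

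| ρ | Change score | Own baseline | Baseline + urn factors, R² 0 | R² 0.1 | R² 0.2 |
|---|---|---|---|---|---|
| 0.3 | 42.2 | 57.3 | 54.1 | 59.1 | 64.2 |
| 0.5 | 42.7 | 51.2 | 48.8 | 52.4 | 58.5 |
| 0.7 | 42.1 | 46.9 | 44.2 | 48.5 | 53.2 |

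The first two power columns are at R² 0 and barely move with R². Half-widths are 0.72 SD for the change score and 0.59/0.64/0.68 SD with own baseline. The mean error of the estimate is within 0.013 baseline SD of zero in every model.

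**4. Urn factors.** Compared with own baseline alone, they change power by about −3, +1 and +6 points at R² 0, 0.1 and 0.2. A second simulation puts the R² 0 cost at 4/3/2 points (58/53/47% to 54/50/45%), so 2 to 4 overall. In a separate run with a single outcome, leaving the factors out gave type I error of 5.1/4.2/3.2/2.6% when they explained 0/0.1/0.3/0.5 of outcome variance. Including them gave 5.4/4.8/4.9/5.5%.

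**5. High correlation.** At ρ 0.8 to 0.9 the own-baseline gain shrinks to about 2 points and then about 0. With non-prognostic urn factors added, the full model gave 41.6% against 42.6%, and 39.0% against 40.4%, for the plain change score.

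**6. Mixed models** (REML, 16 per arm, R² 0, ρ 0.3/0.5/0.7). With complete data and free baseline means, two time points reproduce the change score: 42.5/42.7/41.9%. A common baseline mean gives 60.8/53.9/50.7%, and 55.9/49.6/46.4% with factor-by-time terms. That last model has type I error of 6.6/4.8/6.4% with uncorrected degrees of freedom, so these powers are somewhat flattering and a small-sample correction is needed.

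**7. Other scale.** If d=0.65 is in post-score SD, the change score gives 32/42/63% and the full model 42/48/64% at R² 0.

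**The case against.** The strongest reply is that nothing has been excluded. The covariate list is introduced as examples, naming baseline craving suggests that each outcome's own baseline was intended, and both adjusted and unadjusted analyses are promised. A mixed model with a common baseline mean would already use the baseline, and on that reading the regression proposed here may add no power. This stands. A reader might infer that the plan rules out baseline pain or the urn factors, but the text only leaves the primary model open.

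A reader might also infer bias or a raised false-positive rate. Neither follows: the estimates are unbiased, and omitting prognostic urn factors makes the test conservative.

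The case for the urn factors on precision alone is also modest. It depends on an R² that the documents do not give, and with 32 completers each extra term costs something. The argument for them is chiefly that allocation is balanced on them.

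Finally, low power at d=0.65 is a sample-size matter, and the plan concedes that it may not be fully powered. Even the best case in the table, 64.2%, is below 80%, so covariate choice does not resolve that.

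**Conclusion.** The concern holds in limited form. The HRSD and PHQ-9 passages disagree and must be reconciled before the urn is used. One might read this as meaning that the HRSD will not be collected. The documents show only that it is not scheduled.

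The primary models are under-specified rather than wrong. Under a plain change score, or a mixed model with free baseline means, Aim 2 gives up precision that already-scheduled data would supply: about 42% power against 57/51/47% at ρ 0.3/0.5/0.7, and almost nothing as ρ approaches 0.9. Nearly all the dependable gain comes from the own-baseline term. The urn factors break even near R² 0.1. It would be too strong to say that the full model always gains: with ρ of 0.8 or more and non-prognostic factors it can be about 1 point worse than the change score.

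The textual findings are certain. The sizes rest on assumed ρ, R², the scale of d and binary factors.

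**What to change.** 1. **Before enrolment**, make the randomisation text and the schedule agree. Either define the depression factor on the baseline PHQ-9 with a pre-stated cut-off, or schedule the HRSD before randomisation. State the categories of the other two urn factors as well.
2. **For Aim 1 and for each thermal outcome in Aim 2**, name the primary model: post value on arm, that outcome's own baseline and the three urn factors. Make the unadjusted result secondary.
3. **If a mixed model is kept**, constrain the arms to a common baseline mean, enter the urn factors by time, and use a small-sample correction such as Kenward-Roger. Factor-by-time terms without the common baseline do not recover the gain (about 39% power at R² 0).
4. **Fix a short covariate list** in place of the open one.

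The cost is one definition and two sentences of analysis text. No new data are needed if the PHQ-9 is used, since it and baseline sensory testing are already scheduled. The statistical price is one degree of freedom for baseline and three for binary urn factors, the latter costing about 2 to 4 points of power if they are not prognostic.

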To date there has been limited work examining the effect of rTMS on craving or pain in individuals with OUD. Drawing from the published literature suggesting that excitatory rTMS applied to the DLPFC can reduce both pain and craving, our group completed a preliminary sham-controlled crossover study in prescription OUD patients with chronic pain. Our data suggest that a single session of excitatory DLPFC rTMS *acutely* decreased opiate cue induced craving and thermal pain sensitivity in this group. The promising results from our single session trial parallel the single session results found in nicotine and cocaine use disordered populations

which subsequently translated into positive multiple session clinical trials. As such, it follows that a trial utilizing multiple sessions of rTMS in OUD patients may yield positive results.

The goal of this proposal is to investigate whether multiple sessions of rTMS applied to the DLPFC result in decreased craving (Aim 1) and pain (Aim 2) in treatment-seeking opiate users with or without chronic pain, who are currently hospitalized for opiate detoxification. Additionally, we will follow participants for four weeks to determine if treated participants have a higher rate of abstinence than un-treated participants (Exploratory Aim). These aims will be addressed through a double-blind, randomized, sham-controlled study. 40 participants (20/group) admitted to an inpatient community treatment facility for opiate detoxification will be given 18 sessions of either active or sham rTMS applied to the DLPFC, in an accelerated fashion over three days (6-sessions each day).

Aim 1: Determine if a course of excitatory rTMS applied to the DLPFC results in reduced cue-induced craving. We hypothesize that patients receiving active rTMS will have a greater reduction in cue induced craving (post-treatment vs. pre-treatment) as compared to those receiving sham rTMS. Cue craving will be assessed using a standardized measure (21) during a validated opiate cue paradigm (22).

Aim 2: Determine if a course of excitatory rTMS applied to the DLPFC results in decreased pain. We hypothesize that patients receiving active rTMS will have a greater reduction in pain (post-treatment vs. pretreatment) as compared to those receiving sham rTMS. Pain will be assessed using clinically relevant subjective measures (23, 24). We will also assess pain using a validated quantitative sensory testing paradigm.

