D. RESEARCH DESIGN AND METHODS (including data analysis) C: Approach: General Overview (Figure 1): Our primary aims are to determine if 18 sessions of 10 Hz DLPFC rTMS decreases cue induced opiate craving (Aim 1) and decreases pain (Aim 2) in individuals with OUD with, or without chronic pain, Participants will be recruited from an inpatient unit for opiate detoxification. The majority of this study will take place over a 5-day period during which both primary aims will be accomplished. In an exploratory fashion we will also collect data at one, four, and 12 weeks following discharge to determine the interventions effect on substance use and pain. Acute Phase: We will screen, consent, enroll, and assess participants during an enrollment session which will occur following either a buprenorphine or methadone induction. The morning following induction, prior to their daily dose of buprenorphine or morphine, each participant will be randomized, and undergo both a opiate drug cue-craving paradigm, an inhibitory control/delay discounting paradigm, and a quantitative sensory testing paradigm (as outlined below). Participants will then receive a total of six sessions of rTMS on three consecutive days during the acute phase of the study (18 total treatments). On the day of discharge, prior to a final dose of buprenorphine or methadone, and several hours prior to actual discharge, the prescription opiate cue-craving, inhibitory control/delay discounting paradigm, and quantitative sensory testing paradigms will be repeated. Daily craving will be assessed during visual cue presentations, and daily pain will be assessed using validated questionnaires. Continuation Phase: Participants will either return in person, or receive a phone call at one and four weeks for follow-up for the collection of clinical substance use and pain outcomes. Additionally, the South Carolina Reporting and Identification Prescriptions Tracking System (SCRIPTS), will be accessed once, three months following the hospital discharge.

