The study procedures will also not interfere with any of the standard of care pharmacotherapy commonly delivered during detoxification. There is no known added risk of rTMS during a buprenorphine/methadone taper (in our pilot trial several of our participants were stabilized on buprenorphine). The commonly used non-opiate medications including acetaminophen, hydroxyzine, and cyclobenzaprine, will be allowed during this study (but be held for at least 5 hours prior to each pain assessment). Patients being treated for OUD commonly have co-morbid symptoms of depression and anxiety (58). Subsequently, the initiation of antidepressant medications is common in the acute treatment setting, and will be allowed during this trial (and are commonly used safely with concurrent rTMS).

Inclusion Criteria:

- 1: Participants must be able to provide informed consent and function at an intellectual level sufficient to allow accurate completion of all assessment instruments.
- 2: Participants must meet DSM-5 criteria for moderate or severe OUD. While individuals may also meet criteria for use disorders of other substances (with the exception of alcohol or benzodiazepines), they must identify prescription opiates as their primary substance of abuse.
- 3: Participants must be admitted to the inpatient unit for opiate detoxification.
- 4: Participants must consent to random assignment.

Exclusion Criteria:

- 1: Participants who are pregnant will be excluded.
- 2: Participants with a history of/or current psychotic disorder will be excluded.
- 3: Participants with a history of dementia or other cognitive impairment will be excluded.
- 4: Participants with active suicidal ideation, or a suicide attempt within the past 90 days will be excluded.
- 5: Participants with contraindications to receiving rTMS (including a history of seizures, or any implanted metal above the neck) will be excluded.
- 6: Those with unstable general medical conditions will be excluded.
- 7: Those who are currently using naltrexone, or tramadol, will be excluded.
- 8: Those with alcohol or benzodiazepine use disorders will be excluded due to increased risk of seizure.

Schedule of Visits and Assessments:

	Assessment Domain	Baseline	Post	1 and 4 week F/U	3-Month SCRIPTS Review	
Screening and Enrollment Eligibility:						

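### No depression score is specified at Post, so the depression-adjusted models cannot show whether mood change explains an effect on cue craving, thermal pain or acute-phase pain

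*Combined protocol and SAP*

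**What the plan says.** The Statistical Analysis section states "we will also examine models that do and do not control for changes in depression scores". The stated purpose is to find out whether rTMS affects craving and pain by lowering depressive symptoms. The section does not say which depression scale, which outcomes or which visits these models cover.

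On timing, the General Overview in section D says "The majority of this study will take place over a 5-day period during which both primary aims will be accomplished". Of the later data it says "In an exploratory fashion we will also collect data at one, four, and 12 weeks following discharge".

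Two depression scales are named. The Schedule of Visits and Assessments lists the "Patient Health Questionnaire Nine (PHQ9)(60): Self-Report measure of depressive symptoms", with marks at Baseline and at the 1 and 4 week follow-up and an empty Post cell. The HRSD appears once, under Randomization, as a baseline urn covariate, and it has no row in the schedule. The MINI is a diagnostic interview given at baseline.

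On outcomes, the Aim 2 block of the schedule gives "Primary outcome: Change score in thermal pain threshold and pain tolerance". Sensory testing is marked at Baseline and Post only. The craving scale is given with the cue paradigm at Baseline and Post. It is repeated at 1 and 4 weeks, "but there will be no cue provocation". The Brief Pain Inventory (BPI) and McGill questionnaire are given daily in the acute phase and at both follow-ups.

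**The concern.** To ask whether a treatment effect on an outcome runs through mood, mood change has to be measured no later than the outcome. For cue craving and thermal pain, the outcome is a change from Baseline to the day of discharge. The only depression change the plan provides ends one or four weeks after that day. Followed as written, the models would adjust the main outcomes for something measured after them.

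What is at stake is the interpretation of a secondary analysis. If rTMS reduces craving partly through mood, a later score will tend to show too little of that pathway, and the team may conclude that the effect is largely independent of mood. The plan says that estimates from its unadjusted and adjusted analyses will inform a larger trial, so such a reading could carry forward.

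**Working it through.** **1. Timing, set side by side (from the schedule and the General Overview)**

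| Measure | Baseline | Post | 1 and 4 weeks |
|---|---|---|---|
| PHQ-9 | yes | not marked | yes |
| HRSD (Randomization text) | yes | not named | not named |
| Cue-induced craving | yes | yes | no (uncued craving only) |
| Sensory testing, incl. thermal pain | yes | yes | no |
| BPI/McGill | yes | yes, and daily | yes |

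A Baseline-to-Post depression change cannot be formed from the specified assessments. The General Overview names craving and pain as the daily acute-phase measures, not mood. The gap covers cue craving, sensory testing and acute-phase BPI/McGill. It does not cover BPI/McGill or uncued craving at 1 and 4 weeks, where the PHQ-9 is collected.

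**2. Could the empty Post cell be a table-reading error?** This is unlikely. In the same table the SOWS, sensory testing and craving-scale rows fill the Post cell, while the PSQI, WPAI and RAND-36 rows show the same pattern as the PHQ-9.

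**3. How much a later score could miss (illustration)**

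The documents give no mood effect and no correlations, so every input below is assumed except the total effect of d = 1.0, which is the plan's own detectable effect.

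- T = arm (0 or 1). Post mood M = 1.0·T + e, with within-arm SD 1.
- Outcome Y = 0.5·T + 0.5·M + u. The total effect is 0.5 + 0.5 × 1.0 = 1.0, and the true mediated share is 0.5/1.0 = 50%.
- Later mood W has within-arm SD 1 and within-arm correlation k with M. Its treatment effect is p, the fraction of the Post mood effect that persists.
- Within arm, the slope of Y on W is 0.5·k. Adjusting for W therefore moves the treatment effect by 0.5·k × p.

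| k | effect persists fully (p = 1): 0.5k | effect fades by k (p = k): 0.5k² | effect gone (p = 0) |
|---|---|---|---|
| 0.3 | 15% | 4.5% | 0% |
| 0.5 | 25% | 12.5% | 0% |
| 0.7 | 35% | 24.5% | 0% |
| 0.9 | 45% | 40.5% | 0% |

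A Post score would show 50%. Simulation agrees with the full-persistence column (0.149, 0.252, 0.351, 0.452). Correlation and persistence are separate unknowns, so all three columns are needed.

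**4. What a Post score would not repair**

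Suppose there is no mediation and mood responds to the outcome: Y = T + e and M = r·Y + noise, each with within-arm SD 1. The slope of Y on M is r and the treatment effect on M is r·1.0, so adjustment moves the effect by r². For r = 0.3, 0.5 and 0.7 that is 9%, 25% and 49%. The result is the same whether M is taken at Post or later.

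**5. Precision**

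The plan expects at least 32 completers, or 16 per arm. With a true difference between models of 0.50 and a Post score, the simulated difference had a 95% range of 0.10 to 1.06. With a later score at k = 0.5 and the effect fading by k, the mean was 0.125 and the range -0.09 to 0.48.

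**The case against.** **The schedule is not fully reliable.** The HRSD is needed for randomization but has no row. The Go/NoGo row has no marks, although the text places the inhibitory-control task at baseline and discharge. Follow-up craving is described in words but not marked. An empty cell is therefore limited evidence that nothing is collected. This stands, and it limits the claim: no Post depression score is specified. A reader might infer that none will be taken, and the documents do not establish that.

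**The planned sentence is modest.** It speaks of an attempt, names craving and pain in general, and does not name cue craving or thermal pain. Both constructs have outcomes at 1 and 4 weeks that coincide with the PHQ-9, and Aim 2 relies on the BPI and McGill as well as sensory testing. So part of the analysis is feasible, and it would be wrong to say that the mood question cannot be addressed at all. But the plan places both primary aims in the 5-day period and calls the later data exploratory, so the follow-up analyses do not close the gap for the main outcomes.

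**The repair buys little precision and no causal direction.** Both points are true (steps 4 and 5). They argue for exploratory labelling. They do not justify adjusting for a score taken after the outcome.

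Three stronger readings are tempting, and none is supported:

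- A reader might infer that the timing gap can bias the answer in either direction. False mediation was shown only under reverse causation, which is the same with a Post score. What the timing itself adds in the illustration is understatement.
- A reader might infer that new antidepressants spoil the later score in particular, because "the initiation of antidepressant medications is common in the acute treatment setting, and will be allowed during this trial". The documents give no onset and no frequency by arm, and a start in the acute setting could also affect a Post score. The point does not separate the two timings.
- A reader might infer that the efficacy results are at risk. The unadjusted comparisons use no depression score.

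**Conclusion.** The concern holds within limits. As specified, the plan cannot show whether mood change produced an effect on cue craving, thermal pain or acute-phase BPI/McGill, because no depression score is specified at Post. The later score will tend to understate a true mood pathway. In the illustration a true 50% share appears as anything from 45% down to 0%, depending on a correlation and a persistence that the documents do not give. The actual size cannot be estimated.

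The conclusion rests on the schedule as printed and on the absence of any other depression measure in the text. The impact is modest: this is a secondary analysis in a small developmental trial, and the active-versus-sham comparisons are untouched. The change is still worth making, because it is cheap and a missed Post score cannot be recovered later.

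**What to change.** Choose one of two routes.

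- **Add the score.** Give one brief depression self-report, with identical wording at Baseline and Post and a recall period short enough to fit the acute phase. Use its Baseline-to-Post change in the adjusted models for Post outcomes. The cost is a few minutes at two existing visits. Both already carry the cue, inhibitory control/delay discounting and sensory testing sessions, and the form may be a further scale beside the PHQ-9 and HRSD. It does not remove reverse causation.
- **Restrict the analysis.** State that the depression-adjusted models apply only to the 1 and 4 week outcomes (BPI/McGill and uncued craving), and draw no mood-mediation conclusion for cue craving, thermal pain or acute-phase pain. The cost is one sentence and no participant time, but the question goes unanswered for the main outcomes.

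Under either route, name the depression scale, label the analysis exploratory, report the difference between the models with a confidence interval, and make no causal mediation claim.
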